7.1.4.2 Evaluation of Non-Target Lesions

Complete Response (CR): Disappearance of all non-target lesions. All lymph nodes should be non-pathological in size (<10 mm short axis)

Non-CR/Non-PD: Persistence of one or more non-target lesion(s)

Progressive Disease (PD): Appearance of one or more new lesions and/or unequivocal progression of existing non-target lesions.

Although a clear progression on non-target lesions in absence of stable target lesions is exceptional, the opinion of the treating physician should prevail in such circumstances.

7.1.4.4 Treatment Beyond Progression

Accumulating evidence indicates a minority of subjects treated with immunotherapy may derive clinical benefit despite initial evidence of PD.

Subjects will be permitted to continue study treatment beyond initial RECISTv1.1 defined PD, assessed by the investigator, as long as they meet the following criteria:

- Investigator determined clinical benefit
- Tolerance of study drug
- Stable performance status
- Treatment beyond progression will not delay an imminent intervention to prevent serious complications of disease progression (e.g., CNS metastases)
- Tumor markers are stable/improving, if expressed

A radiographic assessment/ scan should be performed within 4-8 weeks of initial investigator-assessed progression to determine whether there has been a decrease in the tumor size or continued PD (termed irPD). The assessment of clinical benefit should be balanced by clinical judgment as to whether the subject is clinically deteriorating and unlikely to receive any benefit from continued treatment.

If the investigator feels that the subject continues to achieve clinical benefit by continuing treatment, the subject should remain on the trial and continue to receive monitoring according to the Study Calendar (see Table 6.2).

For the subjects who continue study therapy beyond progression, further progression is defined as an additional 20% increase in tumor burden with a minimum 5 mm absolute increase from time of initial PD. This includes an increase in the sum of diameters of all target lesions and/ or the diameters of new measurable lesions compared to the time of initial PD. Study treatment should be discontinued permanently upon documentation of further progression (i.e. irPD).

## 7.1.5 Duration of Response

Duration of overall response: The duration of overall response is measured from the time measurement criteria are met for CR or PR (whichever is first recorded) until the first date that recurrent or progressive disease is objectively documented (taking as reference for progressive disease the smallest measurements recorded since the treatment started).

Duration of stable disease: Stable disease is measured from the start of the treatment until the criteria for progression are met, taking as reference the smallest measurements recorded since the treatment started.

# 7.1.6 Progression-Free Survival

Progression-free survival (PFS) is defined as the duration of time from start of treatment to time of progression.

# 7.2 Safety/Tolerability

Analyses will be performed for all patients having received at least one dose of study drug. The study will use the CTCAE version 5.0 for reporting of non-hematologic adverse events (http://ctep.cancer.gov/reporting/ctc.html).

#### 8.0 ADVERSE EVENTS

## 8.1 Adverse Event Reporting Requirements

Adverse event (AE) monitoring and reporting is a routine part of every clinical trial and is done to ensure the safety of subjects enrolled in the studies as well as those who will enroll in future studies using similar agents. Data on adverse events will be collected from the time of the initial study treatment administration through 100 days after the last dose of study treatment. Any serious adverse event that occurs more than 100 days after the last study treatment and is considered related to the study treatment or intervention must also be reported. Adverse Events of Special Interest as defined in section 8.2.4 will be collected throughout the subject's participation in the study. Serious Adverse Events (SAEs) will continue to be followed until:

- Resolution or the symptoms or signs that constitute the serious adverse event return to baseline;
- There is satisfactory explanation other than the study treatment for the changes observed; or
- Death.

The investigator is responsible for the detection, documentation, grading and assignment of attribution of events meeting the criteria and definition of an AE or SAE. The definitions of AEs and SAEs are given below. It is the responsibility of the principal investigator to ensure that all staff involved in the trial is familiar with the content of this section.

Any medical condition or laboratory abnormality with an onset date before initial study treatment administration is considered to be pre-existing in nature. Any known pre-existing conditions that are ongoing at time of study entry should be considered medical history.

All events meeting the criteria and definition of an AE or SAE, as defined in Section 8.3, occurring from the initial study treatment administration through 100 days following the last dose of the study treatment must be recorded as an adverse event in the patient's source documents and on the CRF regardless of frequency, severity (grade) or assessed relationship to the study treatment or intervention.

In addition to new events, any increase in the frequency or severity (i.e., toxicity grade) of a pre-existing condition that occurs after the patient begins study treatment is also considered an adverse event.

#### 8.2 Definitions

## 8.2.1 Adverse Event

An adverse event (AE) is any untoward medical occurrence in a patient receiving study treatment and which does not necessarily have a causal relationship with this treatment. An AE can be any unfavorable and unintended sign (including an abnormal laboratory or vital sign finding which requires protocol treatment to be modified), symptom, or disease temporally associated with the use of an experimental intervention, whether or not related to the intervention.

- Diagnostic and therapeutic non-invasive and invasive (i.e., surgical)
  procedures will not be reported as adverse events. However, the medical
  condition for which the procedure was performed must be reported if it meets
  the definition of an adverse event unless it is a pre-existing (prior to protocol
  treatment) condition.
- Anticipated fluctuations of pre-existing conditions, including the disease under study, that don't represent a clinically significant exacerbation or worsening, are not considered AEs.

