# Management of Rucaparib Treatment-Emergent ALT/AST Elevations:

- Grade 4 ALT/AST elevations: hold rucaparib until values have improved to Grade 2 or better, then resume rucaparib with a dose reduction. If toxicity is ascribed to nivolumab alone then you may resume without a dose reduction. Monitor liver function tests weekly for 3 weeks after rucaparib has been restarted.
- Grade 3 ALT/AST elevations, in the absence of other signs of liver dysfunction, should be managed as follows:
  - o Monitor liver function tests weekly until improvement to ≤ Grade 2.
  - Continuation of rucaparib with elevation of ALT/AST up to Grade 3 is permitted provided bilirubin is < ULN.

  - If patient has Grade 3 ALT/AST elevation and continues on rucaparib, and levels do not decline within 2 weeks or they continue to rise, treatment interruption and resolution to ≤ Grade 2 will be required before rucaparib can be resumed, either at the current dose or at a reduced dose.

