#### Management of Creatinine Elevation:

- Rucaparib can cause creatinine elevation of any grade in 92% of the patients
   (1% grade 3-4) possibly due to potent inhibition of the MATE1, MATE2-K and
   OCT1 transporters. The majority of reported grade 1-2 creatinine elevations
   stabilize with continued rucaparib treatment without dose modification. However,
   grade 2 elevation of creatinine can also be due to autoimmune nephritis from
   nivolumab. To help identify whether rucaparib or nivolumab is the underlying
   etiology for the creatinine elevation all subjects will undergo repeat CMP on cycle
   1 day 8.
  - Grade 2 creatinine elevation on cycle 1 day 8: Hold rucaparib and recheck on cycle 1 day 15. If creatinine is improved to grade 1 (≤1.5 x ULN) on day 15, then resume rucaparib at full dose.
  - Grade 3-4 creatinine elevation: Hold rucaparib and consider a dose reduction.

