#### 11.4 Data Analyses Plans

The primary endpoint is the progression-free survival proportion measured after 4 months of study treatment for patients in the IIT population. This endpoint is defined as the proportion of evaluable patients alive and progression-free after 4 months of study treatment in the event of no loss to follow-up and/or early patient discontinuation. The outcome is expected to be observed for each patient. In the event that either loss to follow-up or early discontinuation occurs (either not secondary to toxicity), the 4-month PFS will be estimated using the product-limit method of Kaplan and Meier. Follow-up time will be defined as time from the date of first study treatment (PFS1) and 1st line platinum-based therapy (PFS2) until the date of radiological (as per combined RECIST v1.1 and irRECIST criteria) or clinical progression (leading to withdrawal from the study treatment), or loss to follow-up due to toxicity or non-compliance with study procedures, or death from any cause, whichever comes first. Follow-up time will be censored at the date of last disease evaluation. Estimates for the median and 75th percentiles with 95% confidence intervals will be reported. In order to adjust for the patient's exposure to primary platinum-based therapy, a secondary analysis will utilize the Cox proportional hazards model with exposure time entered as an adjustment covariate as either a continuous covariate or as 4 months of exposure versus more than 4 months of exposure. OS will be similarly estimated and summarized with follow-up time calculated from the date of first study treatment (OS1) and 1st line platinum-based therapy (OS2) until date of death or censoring. ORR will be determined as per the irRECIST guidelines for the IIT population. Other safety data (e.g., laboratory safety parameters, vital signs, and new physical examination findings) will be summarized descriptively for the IIT population by reporting counts and percentages, with exact binomial confidence intervals where appropriate. Adverse events will be reported per the NCI Common Toxicity Criteria for Adverse Events (CTCAE) version 5.0.

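### Section 8.2.1 can be read as a treatment-change threshold for laboratory AEs, so whether some laboratory toxicity counts depends on the investigator's action rather than on its grade

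*Combined protocol and SAP*

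**What the plan says.** Section 8.2.1 opens broadly: "An adverse event (AE) is any untoward medical occurrence in a patient receiving study treatment". It goes on to cover any unfavorable and unintended sign, and there it mentions laboratory values once, in a parenthesis: "including an abnormal laboratory or vital sign finding which requires protocol treatment to be modified".

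Section 8.1 requires recording at any grade and any attribution, but only for events that meet the AE definition. For that definition it points to Section 8.3, although the definition is in 8.2. It also says: "Any medical condition or laboratory abnormality with an onset date before initial study treatment administration is considered to be pre-existing in nature". It then counts as an AE "any increase in the frequency or severity (i.e., toxicity grade) of a pre-existing condition that occurs after the patient begins study treatment". That clause has no treatment-change condition.

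Section 5.2 lets some laboratory toxicity be managed with treatment unchanged. For transaminases: "Continuation of rucaparib with elevation of ALT/AST up to Grade 3 is permitted provided bilirubin is" below ULN. For creatinine, it says that most reported Grade 1-2 elevations "stabilize with continued rucaparib treatment without dose modification".

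On analysis, Section 11.1 lists the incidence of AEs as a secondary endpoint, and 2.2.2 makes safety a secondary objective. Section 11.4 adds: "Other safety data (e.g., laboratory safety parameters, vital signs, and new physical examination findings) will be summarized descriptively for the IIT population", as counts and percentages. It names no grade, baseline, worst value or shift.

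**The concern.** If every abnormal laboratory value were already an AE, the qualifier in 8.2.1 would do no work. A site that reads it as a threshold is therefore reading it sensibly. On that reading, what makes a new laboratory abnormality an AE is what was done about it. A Grade 3 ALT rise in a patient whose rucaparib is interrupted is an AE. The same value in a patient who continues, as 5.2 permits, is not.

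The AE table is the plan's main output on the safety of this combination, in 32 patients at 3 sites. If the sites read the parenthesis differently, or act differently where 5.2 leaves discretion, hepatic, renal and marrow AE percentages would differ for reasons unrelated to toxicity. A low percentage could then mean little toxicity, or toxicity that was treated through.

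**Working it through.** The plan states no figure that depends on this definition, so there is nothing to reproduce. The check sets the sections side by side and then gauges scale from the creatinine rates in 5.2.

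**1. Which new-onset abnormalities meet the qualifier under 5.2?**

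| Laboratory abnormality | Section 5.2 | AE on the threshold reading? |
|---|---|---|
| Grade 3-4 haematologic, including Grade ≥3 anaemia | rucaparib held | yes |
| Grade 4 ALT/AST | held | yes |
| Grade 3-4 creatinine | held | yes |
| Grade 2 creatinine on cycle 1 day 8 | held | yes |
| Grade 3 ALT/AST, bilirubin below ULN, no other sign of liver dysfunction | may continue; interruption required if not declining within 2 weeks or still rising | only if interrupted |
| Other Grade 1-2 creatinine | most need no dose modification | only if treatment is changed |
| Grade 1-2 cytopenias, thyroid or lipase changes | no required hold; hold for unremitting Grade 2 at investigator discretion | only if treatment is changed |

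The exposed group is the last three rows.

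**2. Does DILI reporting catch the Grade 3 ALT/AST case?** Continuation at Grade 3 requires bilirubin below ULN. Potential DILI (8.2.3) requires bilirubin above 2 x ULN. Both cannot hold at the same time, so a Grade 3 rise is not a potential DILI while it is being treated through.

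**3. Is the threshold reading consistent with 8.1?** No. A patient who enters with Grade 1 ALT and moves to Grade 2 has an AE under 8.1, whatever happens to the dose. A patient with normal ALT at entry who reaches Grade 3 and continues has none. Both can enroll: 3.1.11 admits AST/ALT up to 3 x ULN, or 5 x ULN with liver metastasis.

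**4. Scale, for creatinine.** Inputs: N = 32 (11.2); any-grade elevation 92% and Grade 3-4 1% (5.2). Hence Grade 1-2 is 92% - 1% = 91%.

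- Any grade: 0.92 x 32 = 29.4 patients.
- Grade 1-2: 0.91 x 32 = 29.1 patients.
- Grade 3-4: 0.01 x 32 = 0.3 patients.

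Let s be the share of Grade 1-2 cases that lead to a treatment change. The documents do not give s, so it is varied. The expected count on the threshold reading is 32 x (0.01 + 0.91 s):

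| Assumed s | Patients with a creatinine AE | Percent of 32 |
|---|---|---|
| 0 | 0.3 | 1% |
| 0.10 | 3.2 | 10% |
| 0.25 | 7.6 | 24% |
| 0.50 | 14.9 | 47% |
| 1 | 29.4 | 92% |

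If every graded elevation counts as an AE, the count is 29.4 whatever s is. The table treats all elevations as new onset. Patients with an abnormal baseline value that worsens would count under 8.1 and raise the lower rows.

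**5. Other analytes.** Section 9.1.9 lists ALT, AST and haemoglobin among abnormalities seen in at least 35% of patients: 0.35 x 32 = 11.2, so at least 11 patients for each. The share managed without a treatment change is not given, so the number left out could be none or all of these.

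**The case against.** The strongest reply is that 8.2.1 says including, which illustrates and does not exclude, under a general clause wide enough for any laboratory abnormality. That is correct. A reader might infer that a laboratory value is an AE only if treatment is changed, but the text does not say so. What stands is that the definition is ambiguous and that the qualifier invites the narrower reading.

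A reader might also infer that the main known rucaparib laboratory harms drop out of the AE table. Section 5.2 contradicts this. It holds rucaparib for most severe laboratory toxicity, and a Grade 3 ALT/AST rise that persists or climbs must also lead to interruption. All of these meet the qualifier on either reading. Worsening baseline abnormalities count under 8.1, and they are foreseeable because patients enter after 4-6 months of platinum therapy.

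Nor are the data lost. CBC, CMP and the footnote 3 tests are scheduled, and 11.4 summarises laboratory parameters. Section 9.1.9 itself lists adverse reactions and laboratory abnormalities separately, so a laboratory table is the natural comparator for its 35% list. This supports putting the main repair in 11.4. It does not make the summary there sufficient, since it is neither graded nor referred to baseline and sits apart from the named endpoint.

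Finally, uneven reporting across sites is a possibility that the wording allows. Nothing in the documents shows that it will happen.

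**Conclusion.** The point holds as an ambiguity with a real consequence. On a reasonable reading of 8.2.1, AE status for some new-onset laboratory toxicity follows investigator action rather than severity, and 8.1 applies the opposite principle to worsening baseline abnormalities. The toxicity affected is mainly low-grade change, plus Grade 3 ALT/AST rises that are continued and then settle.

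The size cannot be fixed from the documents. The range of about 0.3 to 29 of 32 patients for creatinine rests on the 92% and 1% rates in 5.2 carrying over to this trial, on all elevations being new onset, and on an unstated share of Grade 1-2 cases held. It shows how far one row of the AE table could move. It is not an estimate of under-reporting.

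The primary endpoint, sample size and power do not depend on this definition. A reader might infer that the toxicity stopping rule in 11.5 is weakened. That rule counts SAEs, and potential DILI and AEs of special interest are reported as SAEs in their own right, so the documents do not support that inference for those events. This is a cheap improvement that should be made.

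**What to change.** **Section 8.2.1.** Remove the treatment-modification qualifier for laboratory findings of Grade 3 or higher, so that they are recorded as AEs whatever action is taken. State explicitly how lower-grade findings without a treatment change are handled.

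**Section 8.1.** Reconcile the rule on worsening of pre-existing abnormalities with 8.2.1, so that new-onset and worsening values follow one stated principle. Correct the cross-reference for the AE definition from 8.3 to 8.2.

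**Section 11.4.** Derive CTCAE v5.0 grades from the CBC, CMP and footnote 3 results already in the study calendar. For every dosed patient, report the worst post-baseline grade and the shift from baseline for ALT, AST, bilirubin, creatinine, haemoglobin, platelets, neutrophils, lipase and thyroid tests. Name this table as the laboratory toxicity incidence. Where CTCAE v5.0 gives no numeric grade for a test, show the shift against the reference range.

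**Cost.** A short wording change, one programmed table, more AE entries and less favourable AE percentages. Limiting the change in 8.2.1 to Grade 3 or higher keeps the extra entries down: dropping the qualifier at every grade could add entries for up to about 29 of 32 patients for creatinine alone, whereas the graded table captures those cases without AE forms. No new tests are needed, and no dosing or management rule changes.

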#### 8.2.2 Serious Adverse Event

An adverse event is considered "serious" if, in the view of either the investigator or sponsor investigator, it results in any of the following outcomes:

- Death
   If death results from (progression of) the disease, the disease should be reported as event (SAE) itself.
- A life-threatening adverse event
   An adverse even is considered 'life-threatening' if, in the view of either the
   investigator [or sponsor investigator], its occurrence places the patient or
   subject at immediate risk of death. It does not include an adverse event that,
   had it occurred in a more severe form, might have caused death.
- Inpatient hospitalization or prolongation of existing hospitalization for ≥ 24 hours
- A persistent or significant incapacity or substantial disruption of the ability to conduct normal life functions
- A congenital anomaly/birth defect
- O Important medical event
  Any event that may not result in death, be life-threatening, or require
  hospitalization may be considered serious when, based upon appropriate
  medical judgment, they may jeopardize the patient and may require medical
  or surgical intervention to prevent one of the outcomes listed in this definition
  of "Serious Adverse Event". Examples of such medical events include
  allergic bronchospasm requiring intensive treatment in an emergency room
  or at home; convulsions that do not result in inpatient hospitalization or the
  development of drug dependency or drug abuse.

Events or outcomes not qualifying as SAEs:

- Previously planned (prior to signing the informed consent form) surgeries should not be reported as SAEs unless the underlying medical condition has worsened during the course of the study.
- Preplanned hospitalizations or procedures for preexisting conditions that are already recorded in the patient's medical history at the time of study enrollment should not be considered SAEs.
- Hospitalization or prolongation of hospitalization without a precipitating clinical AE (for example, for the administration of study therapy or other protocol-required procedure) should not be considered SAEs. However, if the preexisting condition worsened during the course of the study, it should be reported as an SAE.

Events of progression of the patient's underlying cancer as well as
events clearly related to progression of the patient's cancer (signs and
symptoms of progression) should not be reported as an SAE unless the
outcome is fatal within the safety reporting period.

# 8.2.3 Potential Drug Induced Liver Injury (DILI)

Wherever possible, timely confirmation of initial liver-related laboratory abnormalities should occur prior to the reporting of a potential DILI event. All occurrences of potential DILIs, meeting the defined criteria, must be reported as SAEs.

Potential drug induced liver injury is defined as:

- AT (ALT or AST) elevation > 3 times upper limit of normal (ULN) AND
- Total bilirubin > 2 times ULN, without initial findings of cholestasis (elevated serum alkaline phosphatase)
   AND
- 3) No other immediately apparent possible causes of AT elevation and hyperbilirubinemia, including, but not limited to, viral hepatitis, pre-existing chronic or acute liver disease, or the administration of other drug(s) known to be hepatotoxic.

While treatment is interrupted, the patient should be evaluated for the presence of confounding factors including malignant disease in the liver, co-administration of other suspect drugs, cholestasis, and viral or autoimmune hepatitis that could have caused the laboratory abnormalities. Other laboratory investigations of liver function such as international normalized ratio (INR) should be implemented as indicated. If no alternative cause is identified, rucaparib must be permanently discontinued.

All cases of possible DILI should be followed until all abnormalities have returned to normal, returned to baseline levels, or an alternative cause is found to explain the combination of the increased transaminases and total bilirubin.

